#### 1.8.4 Supportive analyses

Sensitivity analyses for the primary outcome will be performed as follows:

- (A) In addition to the logistic regression model the risk difference for PASI 90 response at Week 52 between Group 1 and Group 2 will be computed with the corresponding 95%-CI (asymptotic Wald CIs with continuity correction) using the SAS PROC FREQ procedure with the RISKDIFFC option.
- (B) The primary analysis (logistic regression analysis) and the analysis of risk difference will be repeated for the PP-P90R set.
- (C) An analysis based on multiple imputations of the PASI 90 response at Week 52 will be performed. Details are described in Section 2.2.3.

#### 1.8.5 Key secondary analyses

Aim of the key secondary analysis, the PASI 90 response rate at Week 52 in the FAS-P75R, is the demonstration of superiority of the shortened 2-weekly dosing group compared to the 4-weekly dosing group in this patient set.

The statistical null-hypothesis to be rejected is that the odds ratio of gaining a PASI 90 response for patients on 2-weekly dosing versus patients on 4-weekly dosing = 1.

Let  $\pi_j$  denote the probability of a PASI 90 response at Week 52 for treatment group j, j=0, 1, where

- 0 corresponds to 2-weekly dosing
- 1 corresponds to 4-weekly dosing

The following hypothesis will be tested

$$H_{02}$$
:  $(\pi_0/(1-\pi_0))/(\pi_1/(1-\pi_1)) = 1$  versus  $H_{A2}$ :  $(\pi_0/(1-\pi_0))/(\pi_1/(1-\pi_1)) \neq 1$ 

This analysis will be performed comparing dosing groups (Group 3 vs. Group 4) with respect to the key secondary variable in a logistic regression model with the factors dosing group, country, body weight at Week 24 (< 90 kg or  $\ge 90 \text{ kg}$ ) and PASI response (< 83% vs.  $\ge 83\%$ ) at Week 24. The odds ratio with its corresponding 95%-Wald CI and the (two sided) p-value of the corresponding Wald statistic will be presented.

In case of subgroup analyses where the grouping variable is one of the above described factors in the logistic regression model the respective factor is excluded from the model.

### 1.8.6 Testing strategy of the primary and the key secondary analysis

**Significance Level:** The primary analysis will be performed at the one-sided 2.5% level which corresponds to a two sided 5% level. Non-inferiority of 6-weekly vs. 4-weekly dosing will be claimed, if the upper limit of the two sided 95%-Wald CI for the odds ratio estimated in the above described logistic regression model does not exceed 2.23. The key secondary analysis will be performed on the two-sided 5% level of significance. The test decision will be based on the Wald test, i.e. if the p-value from the test is below 0.05.

**Multiplicity issues:** The key secondary analysis will be included in the confirmatory testing strategy using a hierarchical testing strategy. The key secondary hypothesis will be a priori ordered below the primary hypothesis. This means that no multiplicity adjustment of the significance level is required; however, confirmatory evidence will be claimed only if non-inferiority with regard to the primary endpoint has been successfully demonstrated before. Otherwise, the result for the secondary endpoint will be interpreted as being purely explorative, independent of the nominal p-value.

#### 1.8.7 Secondary analyses

All secondary efficacy analyses for Treatment Period 2 (and Week 60, if applicable) will be performed by dosing group in the FAS-P90R and the FAS-P75R, separately.

# PASI 50/75/90/100 and IGA mod 2011 0 or 1 response over time in Treatment Period 2 and Follow-Up Period

Summary statistics for PASI 50/75/90/100 response and for IGA mod 2011 0 or 1 response from Week 24 to Week 52 will be presented for the FAS-P90R and the FAS-P75R separately in contingency tables including absolute and relative frequencies. For the FAS-P75R also the response rates at Week 60 will be provided. Risk differences between the dosing groups will also be provided.

Figures will be provided as well displaying estimates for responder rates by dosing group.

#### PASI score over time in Treatment Period 2 and Follow-Up Period

Summary statistics will be provided for absolute PASI scores as well as for absolute and percent change from baseline by visit and treatment group. The analysis will be performed until Week 52 in the FAS-P90R and until Week 60 for the FAS-P75R. Figures for mean course of the PASI score will also be provided.

The absolute PASI score will be analyzed by analysis of covariance (ANCOVA) models with dosing group, country and body weight stratum as explanatory variables and baseline value as covariate. ANCOVAs will be performed at each visit starting with Week 28.

## DLQI, EQ-5D, WPAI-PSO and assessment of pain, itching and scaling in Treatment Period 2

For the DLQI subscale and the DLQI total score, the EQ-5D VAS and the EQ-5D utility index, for each of the main outcomes of the WPAI-PSO and for the assessment of pain, itching and scaling, the absolute and percentage change from baseline to each visit during

Treatment Period 2 where the scales are assessed will be derived. Summary statistics will be provided for absolute values as well as for the percentage change by visit and dosing group.

Page 32

ANCOVA models with dosing group, country and body weight stratum as explanatory variables and baseline value as covariate will be performed for the visits Week 36, 48 and 52.

In addition, summary statistics will be provided for number of subjects achieving DLQI 0 or 1 at each visit where the DLQI is assessed. Risk differences including 95%-CIs will also be presented for the visits Week 36, 48 and 52.

For the single EQ-5D dimensions contingency tables will be provided for each visit where the scale was to be assessed. Changes from baseline to each visit will be displayed using the categories improved, unchanged and worsened in each dimension.

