5.3 Treatment assignment, randomization

At the Screening Visit, every patient will be registered in an Interactive Response Technology (IRT) system. The Investigator or his/her delegate will ensure that the patient fulfills all the inclusion/exclusion criteria. At Baseline, every patient will receive study medication kits assigned by the IRT system.

At the Randomization Visit (Week 24) all patients will be assessed in term of PASI response and eligible patients will be randomized by the IRT system to one of the 4 treatment groups in Treatment Period 2 (Week 24 to Week 52) or withdrawn from the study.

Patients with at least a 90% reduction in PASI score from Baseline will be randomized at Week 24 on a 1:1 basis to Group 1 or Group 2:

- Group 1 (recommended maintenance treatment): secukinumab 300 mg s.c. every 4 weeks (Week 24, 28, 32, 36, 40, 44 and 48).
- Group 2 (experimental dosing maintenance treatment): secukinumab 300 mg s.c. every 6 weeks (Week 24, 30, 36, 42 and 48).

Patients with less than 90% reduction in PASI score from Baseline at Week 24 but achieved at least a 75% reduction in PASI score from Baseline are eligible for dose frequency intensification and will be randomized on a 1:1 basis to either Group 3 or Group 4:

- Group 3 (recommended maintenance treatment): secukinumab s.c. 300 mg every 4 weeks (Week 24, 28, 32, 36, 40, 44 and 48).
- Group 4 (experimental maintenance treatment): secukinumab s.c. 300 mg every 2 weeks (Week 24, 26, 28, 30, 32, 34, 36, 38, 40, 42, 44, 46 and 48).

Patients with a reduction in PASI score from Baseline of less than 75% at Week 24 are not eligible for randomization and will be discontinued from the study. The IRT will assign a randomization number to the patient, which will be used to link the patient to a treatment group and study drug to be dispensed to the patient. The randomization number will not be communicated to the IRT user.

The randomization numbers will be generated using the following procedure to ensure that treatment assignment is unbiased and concealed from patients and Investigator staff. A patient randomization list will be produced by the IRT provider using a validated system that automates the random assignment of Patient Numbers to randomization numbers. These randomization numbers are linked to the different treatment groups, which in turn are linked to medication numbers

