5.5.4 Instructions for prescribing and taking study drug

Secukinumab will be self-administered by patients during the study after the study assessments (including completion of PROs) and scheduled blood samples have been performed.

For Treatment Period 1, all patients will be assigned to the same study drug regimen (300 mg secukinumab s.c. every week for the first 4 weeks, and thereafter every 4 weeks) and will self-administer the study drug at the study site under the supervision and guidance of site personnel at the time-points indicated in Table 5-1. To allow for comparable treatment group data on fixed study visits, patients will be trained for home drug administration prior to Treatment Period 2. If needed, a caregiver can be trained for home administration to provide support to the patient; corresponding training should be documented in the source data at the study center.

For Treatment Period 2, patients will be assigned to 4 different treatment interval groups depending on their PASI response at Week 24. Patients will self-administer their first dose of randomized study drug at Week 24 at the study site under the supervision and guidance of site personnel. Thereafter, patients will self-administer the study drug at either the study site or at home depending on the scheduled study drug administration by study group in Table 5-1 and Table 6-2.

Table 5-1 Timing of study drug administration by study group

_		
	Treatment Period 1	
	(Self-administration at Study Site)	(Self-administration at Home)
All Patients		
All patients	Baseline and	None
	Weeks 1, 2, 3, 4, 8, 12, 16 and 20	
	Treatment	Period 2
	(Self-administration at Study Site)	(Self-administration at Home)
Patients with PASI ≥ 90		
Group 1 (every 4 weeks)	Week 24, 28, 32, 36, 40, 44 and 48	None
Group 2 (every 6 weeks)	Week 24, 36, 48	Week 30, 42
Patients with 75 ≤ PASI < 90		
Group 3 (every 4 weeks)	Week 24, 28, 32, 36, 40, 44 and 48	None
Group 4 (every 2 weeks)	Week 24, 28, 32, 36, 40, 44 and 48	Week 26, 30, 34, 38, 42 and 46

Study drug will be dispensed and self-administered with the support of qualified personnel during office visits in accordance with local laws and regulations or self-administered at home. The blinded assessor for PASI and IGA mod 2011 must not be part of the study drug dispensing or administration process.

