PK blood sample		x						x			х			х			×			x	Samples will be shipped by the sites and stored by the central laboratory. Samples will be shipped to reference laboratories for analysis. Samples need to be taken before dosing.

Page 49

Period	Scr				Tre	atmen	t Perio	d 1					Treatment Period 2						FU	it	Comments
Visit	1	2	3	4	5	6	7	8	9	10	11	12	13	14	15	16	17	18	19	d Visit ^d	
Week	-4 to BL ^e	BL	1	2	3	4	8	12	16	20	24 a, b	28	32	36	40	44	48	52 c	60	cheduled	
Recommended visit window (days)			±2	±2	±2	±2	±5	±5	±5	±5	±2	±5	±5	±5	±5	±5	±5	±5	±5	Uns	
Check self- administration log												S	S	s	S	S	S	S		S	Patients must return the self-administration log along with all dispensed PFS and drug packaging at every visit, if applicable.
Complete Screening period eCRF	Х																				
Complete end of Treatment Period 1 eCRF											х										
Complete end of Treatment Period 2 eCRF																		Х			

Footnotes:

- a Visit 11, patients will have the last assessment for Treatment Period 1 performed prior to administration of study drug.
- b Visit 11 assessments must be completed for patients who discontinue study drug prematurely during Treatment Period 1; patient should then enter the post treatment follow-up period, if applicable.
- c Visit 18 assessments must be completed for patients who discontinue treatment prematurely during Treatment Period 2.
- d Unscheduled visit assessments at discretion of the Investigator.
- e A repeat QuantiFERON® TB-Gold In-Tube test is recommended if the result of the first QuantiFERON® TB-Gold In-Tube test is "indeterminate". The patient must be referred for a follow-up TB work-up (as per local guidelines) if either the first or the repeat test is "positive" or if the results of both tests are "indeterminate". If the first test is indeterminate, the Investigator may decide not to repeat the test and to proceed directly to the work-up, though this is not recommended. The patient will not be eligible for enrollment if "active TB is present "or if "latent TB is present" and is untreated as per local guidelines.

Abbreviations:

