6.4.2 Assessment of total body surface area and psoriasis area and severity

The blinded PASI assessor will complete the PASI assessment as indicated in Table 6-1. Whenever possible, the same blinded PASI assessor should perform this assessment at all visits.

The total BSA affected by plaque-type psoriasis will be estimated from the percentages of areas affected, including head, trunk, upper limbs and lower limbs (see below for full details of the PASI assessment). The following calculations will be done: Each reported percentage will be multiplied by its respective body region corresponding factor (head = 0.1, trunk = 0.3, upper limbs = 0.2, lower limbs = 0.4). The resulting 4 percentages will be added up to estimate the total BSA affected by chronic plaque psoriasis.

The PASI scoring system is further described in Table 6-4.

A PASI score (Fredriksson and Pettersson 1978; Weisman et al 2003; Gottlieb et al 2005) will be derived as indicated in Table 6-4. The head, trunk, upper limbs and lower limbs are assessed separately for erythema, thickening (plaque elevation, induration), and scaling (desquamation). The average degree of severity of each sign in each of the 4 body regions is assigned a score of 0-4. The area covered by lesions on each body region is estimated as a percentage of the total area of that particular body region. Further practical details to help with the assessment are provided below:

- 1. The neck is assessed as part of the head
- 2. The axillae and groin are assessed as part of the trunk
- 3. The buttocks are assessed as part of the lower limbs
- 4. When scoring the severity of erythema, scales should not be removed.

Because the head and neck, upper limbs, trunk and lower limbs correspond to approximately 10%, 20%, 30% and 40% of the BSA, respectively, the PASI score is calculated using the formula:

$$PASI = 0.1 (E_H + I_H + D_H)A_H + 0.2(E_U + I_U + D_U)A_U + 0.3(E_T + I_T + D_T)A_T + 0.4(E_L + I_L + D_L)A_L$$

The keys for the letters are provided in Table 6-4

PASI scores can range from a lower value of 0, corresponding to no signs of psoriasis, up to a theoretic maximum of 72.0.

The Baseline value for analysis of the PASI is collected at Day 1 (Baseline Visit).

Patients require a total BSA affected by plaque-type psoriasis of $\geq 10\%$ and a PASI score of \geq 10% at Baseline to be eligible for this study.

Table 6-4 Psoriasis area and severity index scoring system

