#### 1.4.3 Screening, baseline and post-baseline definitions

Screening refers to any procedures (e.g., checking inclusion and exclusion criteria) performed prior to the date of visit 2. Per protocol, subject informed consent must be obtained prior to performing any study related activity. The date of signing informed consent is the start date of screening period. Any assessment obtained during the screening period will be labeled screening assessment.

Visit 2 is defined as *Baseline* visit. All consecutive visits are labeled according to the preplanned study week where they occur, i.e. Week 1, Week 2, and so on.

Week 24 is defined as the end of Treatment Period 1 (visit 11) for patients without premature discontinuation during Treatment Period 1. For patients with premature termination within Treatment Period 1 the last visit is defined as end of Treatment Period 1.

Week 52 is defined as the end of Treatment Period 2 (visit 18) for patients without premature discontinuation during Treatment Period 2. For patients with premature termination in Treatment Period 2 the last visit is defined as end of Treatment Period 2.

Any visits and assessments occurring after the end of Treatment Period 2 visit (Week 52 in the eCRF) will be aligned to the Week 60 Follow-Up visit.

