#### 1.4.5 Multiple assessments within visit windows

When there are *multiple assessments* in a particular visit window, the following rules are applied to select one value "representing" the subject in summary statistics in a visit window.

For baseline assessment definition see Section 1.4.3. For post-baseline visit windows the following applies (unless otherwise specified):

• for *quantitative variables*, the *closest* to the actual visit is chosen. If two assessments have the same distance, then the earlier one will be chosen.

\*\* Data assessed after the date of the Week 24 dose will not be considered as "Week 24 data"

- for *qualitative variables*, the *worst* record is selected. It is noted that in the analyses performed, *worst* case is always well defined (e.g., for urine protein values "+" and "++", the worst case is defined as "++")
- in case qualitative variables are based on quantitative variables, e.g. PASI 75 response, the
  visit will be assigned to the quantitative variable, and this visit will be used for the derived
  qualitative variable

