#### 2.1.2 Analysis of variance/covariance

Analysis of covariance (ANCOVA) will be used with dosing group, country and body weight stratum as explanatory variables and baseline value as covariate. In general, SAS Type III sums of squares will be utilized.

Difference between dosing groups will be determined using least-square means (LSMs) and t-tests using the pooled error term from the linear model. 95% percent CIs for the treatment difference will be calculated based on differences in LSM estimates.

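### The Treatment Period 2 ANCOVAs adjust only for the Day 1 value and leave unused the Week 24 value collected just before the first randomised dose, probably at some cost in precision

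*SAP*

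**What the plan says.** - **Randomisation.** Protocol 5.3: "At the Randomization Visit (Week 24) all patients will be assessed in term of PASI response". Eligible patients are then allocated, after 24 weeks on one common regimen.
- **Model.** For the absolute PASI score at each visit from Week 28, and for the questionnaire scores at Weeks 36, 48 and 52, SAP 1.8.7 specifies ANCOVA with "dosing group, country and body weight stratum as explanatory variables and baseline value as covariate". SAP 2.1.2 gives the same model as the general one.
- **Meaning of baseline.** SAP 1.4.3: "Visit 2 is defined as *Baseline* visit". Protocol 6.4.2 likewise places the PASI baseline at Day 1. No separate baseline for Treatment Period 2 is defined.
- **Week 24 data.** Protocol Table 6-1 schedules PASI and all four patient-reported instruments at Week 24. Under Protocol 5.5.4 the drug is taken "after the study assessments (including completion of PROs) and scheduled blood samples have been performed". Footnote a of Table 6-1 adds: "Visit 11, patients will have the last assessment for Treatment Period 1 performed prior to administration of study drug". The footnote to SAP Table 1-3 says "Data assessed after the date of the Week 24 dose will not be considered as" Week 24 data.
- **Missing data.** SAP 1.8.3 does not replace missing secondary outcomes.
- **Use of Week 24 PASI elsewhere.** The key secondary logistic model (SAP 1.8.5) includes Week 24 PASI response. The imputation model for the primary endpoint (SAP 2.2.3) includes the Week 24 change in PASI.

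**The concern.** In a design that randomises after a run-in, the pre-randomisation value nearest to randomisation is usually a stronger predictor of later outcome than one taken before the run-in. Here that value exists for every ANCOVA outcome and precedes randomised treatment, so adjusting for it is legitimate. The SAP gives no reason for leaving it out of these models while using Week 24 PASI in two others.

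Two things are at stake, both outside the confirmatory hierarchy of SAP 1.8.6. The first is interval width for the mean comparisons of PASI and the patient-reported outcomes. The second is some protection against selective dropout, since the ANCOVAs use whatever outcomes are available at each visit.

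**Working it through.** **Inputs.** The documents give no standard deviation, correlation or power for these ANCOVAs, so there is no planned figure to reproduce. Planned set sizes come from Protocol 9.7 and 9.7.1: 2 × 570 = 1140 for FAS-P90R, and 1580 × 0.133 = 210 for FAS-P75R. All correlations, country counts, missing fractions and employment rates below are assumptions.

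**1. Gain.** Let r be the partial correlation of the Week 24 value with the outcome, given the covariates already in the model. Residual variance is multiplied by 1 − r², and interval width by √(1 − r²).

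| r | width ratio | narrower by about |
|---|---|---|
| 0.1 | 0.995 | 0.5% |
| 0.2 | 0.980 | 2% |
| 0.3 | 0.954 | 5% |
| 0.5 | 0.866 | 13% |

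A simulation of the full model agrees. With n = 210, 10 or 25 countries and a complete covariate, the variance ratios at r = 0, 0.1, 0.2, 0.3 and 0.5 were 1.006, 0.995, 0.965, 0.913–0.915 and 0.755–0.756. With 10% of covariate values missing, filled by a pooled mean with an indicator, they were 1.011–1.012, 1.001–1.002, 0.974–0.976, 0.930–0.931 and 0.785–0.787. With n = 1140, 10 countries and a complete covariate, they were 1.001, 0.991, 0.962, 0.911 and 0.751.

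**2. Cost if the value is uninformative.** With 10 countries the planned model has p = 13 parameters: intercept, group, 9 country terms, weight stratum and Day 1 value. Each added term costs about 1/(n − p − 2) in variance.
- n = 1140: 1/1125 = 0.1%, or 0.2% with a missing indicator.
- n = 210: 1/195 = 0.5%, or 1.0% with an indicator.
- WPAI work scores exist only for employed patients (SAP 1.8.1.3). If half of FAS-P75R were employed, n = 105: 1/90 = 1.1%, or 2.2% with an indicator.

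The break-even r without an indicator is √(1/(n − p − 2)): 0.03, 0.07 and 0.11 respectively. With 10% missing and an indicator it is √(2/(0.9(n − p − 2))): 0.04 at n = 1140 and 0.11 at n = 210.

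**3. PASI after selection on Week 24 response.** In FAS-P90R, Week 24 PASI is at most 10% of the Day 1 score. In FAS-P75R it is above 10% and at most 25%, so it is tied to the Day 1 value already in the model. An assumed lognormal model with this selection, and a latent Week 24 to Week 52 correlation of 0.3 to 0.85, gave:
- FAS-P90R: variance ratio 0.98 to 0.76, intervals 1% to 13% narrower. At latent correlation 0.5 the model's Week 52 PASI 90 rate is 82.3%, close to the protocol's 81.8%, and the gain is 2.5%.
- FAS-P75R: Day 1 and Week 24 PASI correlate at 0.80; variance ratio 1.00 to 0.96, intervals 0% to 2% narrower. This part is illustrative only. The model's Week 52 PASI 90 rates there are 43% to 66%, against 3.8% in Protocol 9.7.1. Both the fit and the gain improve as persistence rises, so a gain above 2% is not excluded.

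**4. Bias.** Simulation with 105 per arm, true effect 0, outcome SD 1, and correlation 0.6 between Week 24 value and outcome:
- Complete outcomes: mean estimate 0.000 (SE 0.140) with Day 1 only; 0.001 (SE 0.112) with Week 24 added.
- Dropout of 30% in one arm for patients with a Week 24 value above 0.5 SD, and 3% otherwise: 0.057 with Day 1 only; −0.001 with Week 24 added.

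**The case against.** The best reply is that this is a preference. Day 1 is the reference for PASI response and for the change-from-baseline summaries, so adjusting for it is coherent and prespecified. Protocol 9.5.1 treats the other secondary variables descriptively and leaves group tests to the SAP, and no precision target exists. The benefit cannot be shown from the documents. It may be slight for PASI, the only one of these outcomes assessed blind. The questionnaires, where more gain is plausible, are open-label (Protocol 5.4), and added precision does not address that.

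Most of this stands and limits the point to an optional improvement. It does not remove it: the data are already held, the break-even correlation is low, and the SAP itself treats Week 24 PASI as prognostic in two other models.

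A reader might infer that a baseline 24 weeks before randomisation biases these comparisons. It does not: both values precede randomised treatment, and with complete outcomes either model is unbiased. Nor may one infer that the comparisons are unbiased without qualification. Step 4 shows that arm-dependent dropout related to Week 24 status can shift the Day 1-only estimate. Whether such dropout will occur is not known from the documents.

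**Conclusion.** The point holds as a cheap, optional improvement. The Treatment Period 2 ANCOVAs omit a pre-randomisation value of each outcome that is already collected. Intervals are probably wider than necessary, by an amount the documents do not allow one to calculate: about 0.5% to 13% for assumed partial correlations of 0.1 to 0.5. The upper figure should not be applied to PASI, where the gain may be only a few percent in FAS-P90R and close to nil in FAS-P75R. The questionnaires may gain more, subject to floor effects.

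The primary and key secondary conclusions are untouched. It would also be wrong to extend the argument to the primary odds-ratio model or the Cox models. Adding a covariate there changes the conditional odds or hazard ratio being estimated, not just its precision, and the 2.23 margin is tied to the primary model as planned.

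**What to change.** In SAP 1.8.7 and 2.1.2:
- Add the pre-dose Week 24 (randomisation-visit) value of the same variable as a covariate in the Treatment Period 2 ANCOVAs, and keep the Day 1 value.
- Take that value from the randomisation visit for every score, PASI and questionnaires alike, whatever analysis window the visit falls in. SAP 1.4.4 re-aligns visits by study day (Week 24 is Day 156–183), so a late or early randomisation visit could otherwise leave no Week 24 value. With a recommended visit window of ±2 days, this should be rare.
- Where the value is missing or undefined, including WPAI work scores in patients not employed at Week 24, use the analysis-set mean pooled over dosing groups plus a missing indicator. No patient is then lost because of the added covariate. Outcome values are still not replaced.
- Leave the primary model, the 2.23 margin, the key secondary model and the Cox models unchanged.

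No new data are needed. One common change covers 18 scores (PASI, 7 DLQI, 3 EQ-5D, 4 WPAI-PSO, 3 rating scales) and about 116 fits: 7 visits × 2 sets = 14 for PASI, plus 17 scores × 3 visits × 2 sets = 102. The statistical downside is the small variance cost in step 2 of the working, incurred only if the Week 24 value proves uninformative.
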